- 2) Parameters of visual function will be investigated by microperimetry testing of contrast sensitivity and the visual field (Goldmann) (e.g., ^{25,33,42}).

The preoperative and postoperative testing will be done on patients with the NIDEC MP1 microperimetry testing system and not the SLO. Microperimetry which is used to test light sensitivity is better for several reasons. First, the examiner can see the fixation point directly. A cluster of blue dots is seen where the patient is fixating. Second, it allows the examiner to do a separate fixation test which can be run in less than a minute. Minimizing patient fatigue during testing increases accuracy of the test. Third, the microperimetry has color photographs and actual fundus tracking which the SLO did not. Fourth, the microperimetry has automated perimetry which the SLO could not do. This increases the repeatability of patient to patient testing at any duration interval. All that is needed is a retinal landmark and the repeat testing spot can be obtained within 0.1 of one degree from the previous testing spot. In addition, there is a library of different types of testing patterns that can be used and, for low vision type situations, as it applies to our patients, there is a feedback training module to train patients to change the preferred retinal focus. The SLO is currently no longer produced. The SLO has poor reliability and is very expensive to maintain.

- 3) Intraocular pressure measurement.
- 4) Slit lamp biomicroscopy for (a) conjunctival reaction, (b) corneal clarity, (c) anterior chamber depth and clarity, (d) iris and pupillary appearance and lens evaluation, and (e) indirect ophthalmoscopy in examining the retinal fundus.
- 5) Fundus photographs and fluorescein angiography studies will be taken preoperatively and at each follow-up visit.

The amount of time required for the follow-up visit will be ca. three hours at each visit postoperatively. It is expected that six postoperative visits in one year will be required.

The criteria for success will be:

1. The donor tissue does not provoke a rejection response in the host or cause an infection. A rejection response will be identified by leaking at the site of the graft with staining on the fluorescein and presence of inflammation in the area of the graft. The presence of inflammation is defined as seeing white edematous retina with fluid over the area of the transplant. This clinical picture would coincide with the hyperfluorescent areas seen as leakage on fluorescein. Scar tissue formation in the parenchyma of the transplant is defined as seeing fibrotic tissue in the retinal pigment epithelium and neurosensory retina in the area of the transplant.

Chronic rejection will be recognized in the clinical examination by scar tissue formation in the parenchyma of the transplant.

2. To determine that the implantation procedure will not have an adverse effect on the host eye. This is obtained by assessing the health of the retina by clinical examination, fluorescein angiography, and to rule out sympathetic ophthalmia in the fellow eye. Immediately prior to implantation, samples of the fluid surrounding the donor tissue will be taken and tested later for sterility, mycoplasma, and endotoxins.

IX. METHODS USED TO IDENTIFY, RECRUIT, AND SELECT SUBJECTS:

Sample size will be ten patients per year with Age Related Macular Degeneration (ARMD). Recruitment of subjects to undergo transplantation will be from the clinical vitreoretinal practice of [name]. Randomization is not an issue in this study as only patients who meet the criteria for macular degeneration loss of vision will be used.

Criteria for selection of patients:

Inclusion Criteria:

- The subject must have decreased central visual acuity of 20/200 or worse in one eye by ETDRS vision testing for a duration of at least one year in the operated eye and have the diagnosis of age related macular degeneration; vision in the nonoperated eye must be better than the operated eye. Vision in the operated eye cannot be better than 20/200.
- Subject is older than 55 years of age
- Patient is willing to return for follow-up visits
- Patient has signed informed consent for retinal transplantation
- Patient has undergone microperimetry and Goldmann visual field testing.

Exclusion Criteria:

- Patient having a central visual acuity of better than 20/200 in one eye by ETDRS or vision worse than 20/200 in one eye by ETDRS for a duration of less than one year
- Unwilling to sign an informed consent
- Patient under 55 years of age
- Patient having medical problems that are contraindicatory for short-term anesthesia

- Patient unwilling to return for follow-up visits
- The patient has been determined to be pregnant by patient history or by pregnancy testing in women of childbearing potential
- Features of any condition other than age-related macular degeneration in the study eye (such as pathologic myopia or presumed ocular histoplasmosis) associated with choroidal neovascularization
- Any significant ocular disease (other than choroidal neovascularization) that has compromised or could compromise vision in the study eye and confound analysis of the primary outcome.
- Inability to obtain photographs to document choroidal neovascularization, including difficulty with venous access
- History of choroidal neovascularization in the study eye
- Participating in another ophthalmic clinical trial or use of any other investigational new drugs within 12 weeks before the start of study treatment
- Prior photodynamic therapy or Macugen therapy for choroidal neovascularization
- Patient who has a history of uveitis, Coat's disease, diabetic retinopathy, glaucoma, or a cataract that prevents visualization of the posterior pole

X. POTENTIAL RISKS:

This research procedure might have unwanted side effects for different reasons.

The known and potential risks for this trial involve standard anesthesia hazards, general and/or local. The surgery would occur under retrobulbar and/or general anesthesia. Surgical complications could result in blindness and/or loss of the eye.

Adverse effects related to the "experimental pilot trial" surgery are: (1) retinal detachment, (2) vitreous hemorrhage, (3) subretinal hemorrhage and/or subretinal proliferative tissue, (4) endophthalmitis, (5) neovascular glaucoma, (6) corneal epithelial defects, (7) cataracts, (8) diplopia, (9) ptosis, (10) prephthisis or phthisis, or (11) possible complications from anesthesia, allergic reaction or side effects from certain medicines.

The adverse effects related to transplantation include (1) the knowledge that the tissue was obtained from an induced abortion may cause psychological stress. (2) There is a possible risk of transmission of viral infection, such as AIDS or hepatitis, from the transplanted tissue. However, blood of the woman having the abortion that has donated the fetal tissue will have been tested for the presence of antibodies against human immunodeficiency virus (HIV, the virus that causes **AIDS**), **hepatitis (Hepatitis B Surface Antigen, Hepatitis C Virus Antibody) and syphilis**. To reduce the risk for virus transmission, aborted tissue from women positive for the above mentioned viruses is excluded. In addition, any donors with any risk factors in their history, such as multiple sex partners, drug use, jail time etc. are excluded (see **Behavior and Risk Assessment Form in Donor Consent**). (3) There is a low possibility of an immunological reaction to the donor tissue. The immunologic reaction to the donor tissue is to be studied. Because we feel there is a low probability of an immunological response to the donor tissue, immunosuppression, either systemic or local, will not be used. Therefore, there is a potential risk of immune rejection of the transplanted tissue.

Sympathetic ophthalmia is a possibility, but the prevalence of sympathetic ophthalmia is difficult to measure because it has always been a relatively rare disease; as a result of improvements in modern surgical and medical treatment it has become even more uncommon. Kilmartin et al. reported in 2000 that the incidence of sympathetic ophthalmia after vitrectomy has increased and is more than twice that of the previously reported 0.06% risk. (Kilmartin et al., Br J Ophthal 84:448, 2000) Vote et al reported in 2004 that after repeated vitreoretinal surgery the risk of sympathetic ophthalmia is approximately 1/800 (=0.125%). Prompt and effective management with systemic immunosuppressive agents permits good control of this disease with retention of good visual acuity (Vote et al., Clin Exp Ophthal 32(5):542, 2004).

The donors will not require an extra blood drawing procedure since the donor sample will come from the same blood sampling procedure that the Women's Surgical Center does for blood typing, antibody screens and complete blood cell count. The extra amount needed for the testing is 10 cc. This poses no additional risk for the donor because the blood drawing has already been done prior to the abortion procedure.

Pregnant and nursing women are excluded as recipients from the study. Pregnancy testing will be done in women of childbearing potential.

It is necessary to be aware that there are additional risks in this procedure that are currently unforeseeable.

XI. POTENTIAL RECIPIENT BENEFITS:

Potential benefits to the age related macular degeneration patients are that vision may be preserved or improved.

Subjects will be informed of any new findings that may influence their willingness to continue their participation in this study. This would apply to findings that have become available after they have signed the consent form but before transplantation.

XII. MONITORING UNANTICIPATED ADVERSE EVENTS:

The principal investigator will monitor the progress of the patients.

All adverse reactions, such as chronic elevation of pressure, intraocular infection and/or delayed wound healing, with or without wound leak sympathetic ophthalmia, will be reported within ten days to the local IRB.

XIII. COMPENSATION COSTS:

The subjects will not be compensated for participating in this surgical procedure. The responsibility for the costs of physician, surgery, and hospital will be covered by funds provided by our anonymous sponsor. Travel for follow-up visits will be at the patient's expense.

XIV. FUNDING:

Funding for this clinical trial has been covered by an anonymous sponsor and the Foundation Fighting Blindness is administering the funds. The latter organization is a non-profit 501-C3 health organization. Its purpose is to support retinal research. It has supported projects at the University of Louisville in the Departments of Anatomy and Ophthalmology since 1983.

XV. CONFIDENTIALITY:

All records regarding the individual patients involved will be maintained in a locked cabinet within the office of [name], [name]. Routine medical confidentiality will apply to all trial records. Use and/or publication of trial results will not involve the use and/or release of patient identities. There is the possibility that the Food and Drug Administration and the Human Studies Committee at Norton Audubon Hospital may wish to inspect the records.

XVI. FETAL RETINAL TISSUE:

The research will be conducted in accordance with the prohibitions regarding the use of human fetal tissue described in Public Law 103-43, section 498B. There will be no compensation for the donor. The research will be conducted in accordance with any applicable State or local laws.

Persons engaged in the proposed studies will have no part in: (i) any decisions as to the timing, method, and procedures used to terminate the pregnancy, and (ii) determining the viability of the fetus at the termination of the pregnancy. The proposed studies will not introduce any procedural changes which may cause greater than minimal risk to the fetus or the pregnant woman into the procedure for terminating the pregnancy.

The fetal tissues used in this study will be derived from dead fetuses at the first 9-16 weeks of pregnancy obtained from elective abortions. The tissue will be harvested at the EMW Women's Surgical Center at Louisville.

After the woman seeking abortion has signed the formal papers for this procedure in the presence of an Attending Counselor, only then will she be asked to donate the aborted tissue and sign the consent form (see Donor Research Subject Information and Consent Form). The decision for an abortion and the signing of the consent form will remain completely independent of each other. The consent form is signed in the presence of an Attending Counselor, and not of the Attending Physician because the Attending Physician is only present for the actual abortion procedure. Before signing, the necessity to give a blood sample (see below) is also discussed. The cost for the blood test will be paid for by the investigator. The Medical History and Behavior Risk Assessment form is completed to assist in excluding different diseases (see Donor Research Subject Information and Consent Form).

Even after signing the consent form, the donor can retract her decision to donate the tissue any time. There will be no benefit to the donor, monetary or otherwise. The donor will remain anonymous to the investigators. There will be absolutely no change in the surgical procedure as a result of the participation in the project.

The attending physician will sign the consent form and will make the determination whether the fetus is dead. Suction abortion procedure will be used that macerates the fetal tissue. The attending counselor and the attending physician will have no connection with the proposed studies (see Donor Research Subject Information and Consent Form).

In the consent form, the donor is also asked to give a blood sample to determine that the tissue is safe for transplantation. The necessity to give a blood sample will be explained to the donor by the Attending Counselor at the same time as she is asked to donate the tissue.

Only tissues that are free from contamination will be considered. A blood sample of the donor will be tested for the presence of antibodies against human immunodeficiency virus (HIV) and hepatitis (HAV, HBV, HCV), HLA complete typing, RPR, and ABO testing. To reduce the

risk for virus transmission, aborted tissue from women positive for the above mentioned viruses is excluded.

The donors will not require an extra blood drawing procedure since the donor sample will come from the same blood sampling procedure that the Women's Surgical Center does for blood typing, antibody screens and complete blood cell count. The extra amount needed for the testing is 10 cc. This poses no additional risk for the donor because the blood drawing has already been done prior to the abortion procedure.

In addition, blood- and tissue typing will be done with a sample of the fetal tissue and the recipient's blood to observe whether donor and recipient are matched in the MHC-antigens. We have done this for the last four patients and donors. No matching in any MHC antigens was observed. Even though there is no blood sample from the fetus, the tissue that was transplanted came from a large section, a piece of which was used for the tissue typing of the donor. The typing of this donor tissue was done by extracting the DNA from the fetal tissue using a QIAGEN DNA extraction kit (Pel Freeze, Brown Deer, Wisconsin) which is specific for tissue and different from the one used for blood typing. The kit allows us to identify specific sequences in the MHC DNA and that allows us to identify the donor tissue MHC sequences.

The following is the **procedure of handling fetal donor tissue**:

Sterile procedures are used at all times including the use of sterile surgical gloves, sterile containers, sterile filtered solutions and sterilized instruments. When possible, instruments, transfer tools, etc., are autoclaved before use. Instruments that cannot be autoclaved, such as the handle of the transfer tool, are sterilized by the Sterrad procedure. The sterilization with the Sterrad procedure consists of a sterilant hydrogen peroxide and gas plasma, at 10-40 degrees centigrade for 75 minutes. This is a standard common procedure at Norton Audubon Hospital. Gloves are changed regularly. Waste tissue is treated as biohazard waste.

1. The tissue is obtained by a sterile abortion procedure, placed into a sterile container and refrigerated. The tissue might have to stay in the refrigerator (4°C) for 1 hour depending on when our assistant, [name], can come and pick it up.
2. The tissue is transported in this container on ice to the Norton Audubon Hospital.
3. In a laminar flow hood in the lab, extraocular tissues are removed, the eyes are dissected from surrounding tissue, and are placed into a sterile plastic 6-well dish, containing cold sterile Hibernate E medium (Supplier Specialty media, Philipsburg, NY) with B-27 supplements (cat. # 17504-044) (Gibco BRL, Baltimore, MD).
In the previous clinical trials, the time from step 1 (abortion) to step 4 (placement in hibernation medium) ranged between 30 and 90 minutes.
4. The retinal tissue is dissected aseptically in a sterile 35 mm dish on a metal cold plate (containing a small ice tray) under a dissection microscope with fiber optics. The blower of the laminar flow hood is constantly left on, and decontaminated with UV light when not in use.
5. Dissection starts at 1 to 2 hours after abortion. During dissection, the tissue is transferred several times into a fresh dish with Hibernate E medium. Two alternative procedures are used:
 - a) *dissection of retina only*: The retina is dissected free from surrounding tissues (sclera, choroid, RPE, cornea, lens and blood vessel layer in vitreous). The dissection of retina only

takes ca. 15-25 minutes.

b) *dissection of retina with RPE*: First, the back of the eye is dissected free from extraocular muscles and connective tissues. Then, the eye is incubated for 30 minutes in sterile dispase (Collaborative Biomedical Products, cat. # 354235) at 37°C in a humidified incubator.

After 3 washes with hibernate E medium, the sclera is removed. The dissection of retina with RPE in the lab takes ca. 45-70 minutes, including the incubation time in dispase.

6. The tissue is transported to the surgery room and kept on ice in Hibernate E medium.
 7. In the surgery room, in a sterile environment, a **second** dissection microscope with its fiber optics has been decontaminated and covered with sterile plastic covers according to standard surgery procedures.
 8. The fine dissection of the RPE (removal of choroid) takes place in the surgery room. This dissection takes ca. 20 – 45 minutes, depending on the size of the eye. Rectangular pieces of retina with or without RPE (1.5 – 2 mm width, 2 – 3.5 mm length) are cut with sterile microscissors. Notes are made regarding the orientation and retinal quadrant from which the pieces are cut.
 9. The piece is loaded into the implantation tool, together with a small spacer (same width, but only 0.2 – 0.4 mm length) close to the mandrel, and handed to the surgeon.
 10. Fluid surrounding the tissue is sent for microbial testing at the hospital; mycoplasma and endotoxin testing will be done at Focus Technologies in Cypress, California.
- In the previous clinical trials, the time from abortion to implantation ranged between 3 and 30 hours.

REFERENCES/PUBLICATIONS:

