Secondly, the human fetal retinal tissue will be placed in the areas beneath the retina where presently the patient has atrophy of the retinal pigment epithelium and poor retinal function.

The specific goals of this study are to demonstrate that:

1. Safety of the procedure by testing with pre-operative and post-operative vision evaluation by ETDRS (Early Treatment Diabetic Retinopathy Study) and microperimetry in patients with age-related macular degeneration and a vision of 20/200 or worse in the operated eye. The level of anticipated visual acuity improvement is unknown, but none of the patients treated thus far have lost acuity in the treated eye to the extent that this can be assessed within the limits of the testing method.

2. To determine that the donor tissue transplanted into the subretinal space will not cause harm to the host eye, the health of the retina will be assessed by clinical examination, fluorescein angiography, and the fellow eye will be examined to rule out sympathetic ophthalmia. Immediately prior to the implantation, the fluid surrounding the donor tissue will be sampled and later tested for sterility, mycoplasma, and endotoxins.

3. To confirm that the donor tissue will not provoke a rejection response in the host. A rejection response will be identified by retinal leaking surrounding the graft with staining on fluorescein and the presence of inflammation in the area of the graft. Chronic rejection would be recognized on the clinical examination by scar tissue formation in the parenchyma of the transplant.

II. DESCRIPTION OF DEVICE

Sheets of human fetal neural retina with its retinal pigment epithelium will be placed beneath the retina with the implantation instrument.

Obviously, the device is the implantation instrument and the fetal donor tissue is a biological tissue and not a device. Because of fetal tissue transplantation being under FDA supervision, the device and fetal donor tissue will be considered under the same IND number, even though the tissue is not per se a device.

III. INTRODUCTION:

The long-term goal of this proposal is to show that retinal transplantation can help to prevent blindness and to restore eyesight.

"Fetal retinal cell transplantation" includes transplantation of fetal neural retina (that will develop photoreceptors) and/or fetal retinal pigment epithelium (RPE) cells. "Retinal pigment

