Our approach will focus on dry age-related macular degeneration. Replacement of degenerating cells by retinal pigment epithelium together with neural retina may offer success in restoring the atrophying neural retina, the pigment epithelium and part of the choroid.

VII. HYPOTHESIS TO BE TESTED:

1. Retinal transplantation by co-grafting sheets of human fetal neural retina with RPE is a safe procedure and will not have any adverse effect on the host eyes when transplanted into the subretinal space.

2. The intact sheet of transplanted human fetal neural retina with its RPE will not provoke a rejection response in the host.

VIII. DESIGN OF THE STUDY:

The participating surgeon will be [name]. The participating persons obtaining fetal retinal and RPE tissues will be [name] and [name]. [name] and [name] will participate as consultants during this project for immunology and electrophysiology testing respectively.

Before surgery, the recipient has to sign a statement that he/she is aware about the source of the donor tissue (see Research Subject Information and Consent Form), and a consent form (see Research Subject Information and Consent Form) in which the study is explained.

Ten patients with ARMD and a vision of 20/200 or worse in one eye will be selected for the study and will undergo an operation to implant fetal neural retina with RPE under the retina. Two complete examinations will be performed at least 30 days apart to confirm the visual acuity, and only one eye will be subject to surgery.

The donor tissue is taken up in a custom-made instrument with a flat, curved nozzle so that the tissue will be maintained in the correct orientation and polarity in the subretinal space of the patient's eye. (U.S. patents # 5,941,250: "Retinal tissue implantation method"; # 6,159,218: "Retinal tissue implantation tool"; # 6,156,042: "Retinal tissue implantation instrument")

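### The rejection definition reads as needing angiographic leakage and clinical inflammation together and leaves an eye with only one of them unclassified, which can under-count rejection in a trial claiming its absence

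*Protocol*

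**What the plan says.** Hypothesis 2 (Section VII) is that the graft "will not provoke a rejection response in the host". Criterion 1 of the criteria for success (Section VIII) makes the same claim of absence and adds absence of infection.

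The case definition appears twice:

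- Section I, specific goal 3: "retinal leaking surrounding the graft with staining on fluorescein and the presence of inflammation in the area of the graft".
- Section VIII, criterion 1: "leaking at the site of the graft with staining on the fluorescein and presence of inflammation in the area of the graft".

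Criterion 1 then spells out the clinical component: "The presence of inflammation is defined as seeing white edematous retina with fluid over the area of the transplant". It links that component to the angiogram: "This clinical picture would coincide with the hyperfluorescent areas seen as leakage on fluorescein". A separate route follows: "Chronic rejection will be recognized in the clinical examination by scar tissue formation in the parenchyma of the transplant".

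The protocol does not name the non-scar form of rejection; below I call it non-chronic. No sentence in either section says what happens to an eye with leakage and staining but no visible inflammation, or the reverse.

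**The concern.** The signs are joined by 'with' and 'and', and no 'or' appears. The natural reading is therefore a conjunction, and the clinical component is itself a compound sign. In a trial that sets out to show a harm is absent, a conjunctive case definition gives up sensitivity for specificity, and each rejecting eye it misses moves the result towards success.

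With about ten eyes, one such classification could decide whether the report says zero rejections. Because the rule for discordant signs is not fixed in advance, that decision would be made after the findings are known.

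By the protocol's own account rejection is a live possibility. Section III describes donor RPE and microglia as immunogenic and reports rejection in earlier RPE-only transplants by others. Section X states that no immunosuppression will be used and that the immunologic reaction is itself under study.

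**Working it through.** **Reading the text.** Leakage with staining can fairly be taken as one angiographic finding. The definition then has two components:

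- A: leakage with staining at the graft on fluorescein angiography.
- B: inflammation at the graft, as defined in criterion 1.

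| Eye shows | Classification in criterion 1 and goal 3 |
|---|---|
| A and B | rejection response |
| A only | not stated |
| B only | not stated |
| scar tissue in the graft | chronic rejection, on its own |
| none of these | no rejection |

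**Direction.** Whatever the dependence between signs, P(A and B) ≤ P(A or B), with equality only if the two always occur together. So the joint rule never yields more rejections than an either-component rule, and the difference is exactly the discordant eyes.

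**Size.** The protocol gives no rejection rate, margin or detection probability, so there is no figure to reproduce. What follows is illustration only.

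Inputs:

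- n = 10 eyes (Section VIII; Section IX says ten per year).
- r = true rejection rate. Assumed, 0.10 to 0.30.
- s = chance that each component is seen in a rejecting eye. Assumed, 0.7 to 0.9.
- One look per eye and no false positives. Assumed.

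Formulas: the chance q that the rule detects a rejecting eye is

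- s² if both components are required and are independent;
- 1 − (1 − s)² if either is enough and they are independent;
- s under either rule if they always coincide.

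The chance that no eye is scored as rejecting is P0 = (1 − r·q)^10.

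At r = 0.20 and s = 0.8:

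- both: q = 0.64, P0 = (1 − 0.128)^10 = 0.254
- either: q = 0.96, P0 = (1 − 0.192)^10 = 0.119
- always coincide: q = 0.80, P0 = (1 − 0.160)^10 = 0.175 under both rules

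| s (r = 0.20) | both required | either enough | always coincide |
|---|---|---|---|
| 0.7 | 0.357 | 0.134 | 0.221 |
| 0.8 | 0.254 | 0.119 | 0.175 |
| 0.9 | 0.171 | 0.110 | 0.137 |

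Over r = 0.10 to 0.30 and s = 0.7 to 0.9, P0 runs from 0.062 to 0.605 with both required and from 0.029 to 0.385 with either enough.

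**Sensitivity of the illustration.**

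- *Three separate signs.* If leakage and staining are counted separately, at r = 0.20 and s = 0.8, q = 0.8³ = 0.512 and P0 = 0.339 with all three required, against 0.110 with any one enough.
- *Repeated looks.* Section VIII has six follow-up visits with angiography at each. With two independent looks, at r = 0.20 and s = 0.8, the joint rule has q = 1 − (1 − 0.64)² = 0.870 and P0 = (1 − 0.174)^10 = 0.148. The either rule has q = 1 − 0.04² = 0.998 and P0 = 0.108. The gap narrows.
- *False positives.* If each component appears without rejection with assumed probability 0.05 or 0.10, independently, ten non-rejecting eyes are free of both with probability 0.95^20 = 0.36 or 0.90^20 = 0.12. An either-component rule used alone would therefore over-call.

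**The case against.** A reader might infer that the protocol scores an eye with partial signs as free of rejection. It does not say so: the definition contains neither 'only' nor 'all of', and such an eye is left unclassified. That part of the objection stands, and the point is limited accordingly.

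A reader might also infer three independent signs and a large bias. The text does not support this either. Leakage with staining may be one finding, and criterion 1 expects the clinical picture to coincide with the leakage. If it always does, the gap is zero. This objection also stands, but the expectation comes with no data, and recording the components separately would test it.

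Third, isolated signs have other routes. Scar tissue alone identifies chronic rejection, and criterion 2, goal 2 and Hypothesis 1 concern harm to the eye, with no joint-sign requirement for the retinal assessment. So an eye with isolated leakage or oedema is not automatically a trial success. But neither route enters that eye in the rejection count on which Hypothesis 2 rests.

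Fourth, requiring concordant signs is a defensible specificity choice after subretinal surgery, and reporting layouts often belong in an analysis plan. Both are fair. They argue against replacing the joint rule, or forbidding a 'no rejection' statement because of a single sign. They do not excuse leaving discordant eyes undefined in a success criterion that the protocol itself fixes.

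**Conclusion.** The point holds in a limited form. As written, the definition reads as requiring the angiographic and clinical components jointly for non-chronic rejection and gives no classification when only one is present. Because the claim is one of absence, a discordant eye that is truly rejecting can only be lost from the count, never added, so the error favours success.

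The size cannot be derived from the protocol. The illustrative contrast of 0.254 against 0.119 rests on an assumed 20% rejection rate, assumed 80% detection per component, independence, a single look and no false positives. Concordant signs or repeated looks shrink it, to nothing if the components always coincide. The documents do not support saying that the trial is built to find no rejection, or that its conclusion would be invalid. This is a cheap improvement to the endpoint definition.

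**What to change.** In criterion 1 (Section VIII) and goal 3 (Section I), with the same wording in both places:

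1. Keep the present conjunction and label it 'definite rejection'.
2. Add 'possible rejection': either component at the graft, meaning leakage with staining or inflammation as criterion 1 defines it, that is new against the preoperative examination.
3. Leave the scar-based definition of chronic rejection as a separate category.
4. Report the definite and possible counts, with each component by eye and visit, beside any statement that no rejection occurred. Possible cases qualify that statement but do not bar it.

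The cost is a few lines of text and one table. Fundus photographs and angiography are already planned preoperatively and at every follow-up visit, so no procedure is added and no clinical management changes. The downside is that some postsurgical leakage will be listed as possible rejection, so the result may look slightly less favourable.
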